Study Protocol and Statistical Analysis Plan

**A Phase I-II Trial of Daratumumab for the
treatment of patients with AL amyloidosis**

Protocol version 12, 2/26/19

Statistical plan pages 15-16

NCT02841033

[name]. PI

BOSTON MEDICAL CENTER

A Phase I-II Trial of Daratumumab for the treatment of patients with AL amyloidosis

Index	Page
Section 1.0 Objectives	2
Section 2.0 Background	2
Section 3.0 Drug Information	3
Section 4.0 Staging Criteria	4
Section 5.0 Recruitment and Consenting	4
Section 6.0 Eligibility Criteria	6
Section 7.0 Treatment Plan or Research Design with guidelines for reporting	8
Section 8.0 Toxicities to be Monitored and Dosage Modifications	10
Section 9.0 Study Calendar	12
Section 10.0 Criteria for Evaluation and Endpoint Definitions.....	13
Section 11.0 Statistical Considerations	15
Section 12.0 Data and Safety Monitoring Plan	16
Section 13.0 References	24
Section 14.0 Appendices	25

PRINCIPAL INVESTIGATOR(S):

CO-INVESTIGATORS:

[name].
Sponsor-Investigator
Section of Hematology and Oncology
Boston Medical Center
[name]
[name]
[contact]
[contact]

[name]
Section of Hematology and Oncology
Boston Medical Center
[name]
[name]
[contact]
[contact]

[name]
Section of Hematology and Oncology
Boston Medical Center
[name]
[name]
[name]
[contact]

[name]
Director of Blood Bank
Boston Medical Center
[name]
[name]
[contact]
[contact]

IND #131818
NCT #NCT02841033

Janssen Scientific Affairs, LLC is providing funding
as well as the study agent daratumumab for this study

Version 1: 5/19/16 Version 2: 6/21/16 Version 3: 8/29/16 Version 4: 9/1/16 Version 5: 9/13/16 Version 6: 2/9/17 Version 6.1: 2/16/17 Version 7: 4/27/17 Version 8: 6/7/17 Version 9: 9/21/17 Version 10: 10/9/17 Version 11: 1/9/19 Version 12: 2/26/19

--

1.0 **OBJECTIVES**

Primary:

- 1.1 Safety and tolerability of infusion of daratumumab in AL amyloidosis, specifically with respect to infusion reactions

Secondary:

- 1.2 Determine hematologic response rate of single agent daratumumab
- 1.3 Determine organ responses with respect to cardiac biomarkers and proteinuria
- 1.4 Determine time to next treatment

Exploratory:

- 1.5 Assess Health Related Quality of Life as reported in SF-36

2.0 **BACKGROUND**

AL amyloidosis is a variant plasma cell disorder in which clonal bone marrow plasma cells produce immunoglobulin light chains that misfold into fibrils that are deposited in visceral organs, leading to organ dysfunction and failure. Untreated, the disease has a median survival of only about one year. Oral treatment with melphalan and dexamethasone has had varying efficacy in different centers^{1,2}. More intensive treatment with high dose intravenous melphalan with autologous stem cell transplantation (HDM/SCT) produces complete hematologic responses (CR) in about 40% of patients and partial responses in a similar proportion; these are frequently accompanied by stabilization or improvement in organ function³. However, less than 30% of referred patients are eligible for HDM/SCT and treatment-related mortality (TRM) is high in inexperienced centers. While hematologic responses can be durable after HDM/SCT, 28% of patients do relapse at a median of 4 years⁴. Thus, we continue to seek more effective regimens for patients who are ineligible for or who have relapsed after first line of therapy.

The advent of novel agents in the treatment of multiple myeloma has changed the therapeutic landscape of plasma cell dyscrasias. Clinical trials at Boston Medical Center incorporating proteasome inhibitors such as bortezomib and ixazomib, as well as immunomodulatory agents including thalidomide⁵, lenalidomide⁶, and pomalidomide have shown promising activity in AL amyloidosis.

Daratumumab is a human CD38-directed monoclonal antibody, recently FDA approved, for the treatment of patients with multiple myeloma who have received at least three prior lines of therapy including proteasome inhibitor (PI) and immunomodulatory agent (IMiD) or who are double-refractory to a PI and an IMiD. Daratumumab led to an overall hematologic response of 29% in heavily pretreated, relapsed or refractory patients with myeloma. The median time to response was 1 month (range, 0.9 to 5.6 months) and the median duration of response was 7.4 months (range: 1.2 to 13.1+ months)⁸. Results were similar in an open-label dose escalation trial of daratumumab monotherapy in patients with relapsed or refractory myeloma. Given the above, daratumumab has become a drug of interest in the field of AL amyloidosis, a disease that shares a similar pathophysiology to multiple myeloma; both are clonal plasma cell dyscrasias expressing CD38 on their surface.

Given these promising results of daratumumab monotherapy in myeloma, we propose a study of daratumumab in the treatment of patients with AL amyloidosis who are in need of a second line of therapy.

3.0 **DRUG INFORMATION**

3.1 Daratumumab (IND-948)

- a. **DESCRIPTION:** Daratumumab is a human CD38-directed monoclonal antibody currently FDA approved for the treatment of patients with multiple myeloma who have received at least three prior lines of therapy including a proteasome inhibitor (PI) and an immunomodulatory agent or who are double-refractory to a PI and an immunomodulatory agent. Daratumumab is a human IgG1k monoclonal antibody that binds the CD38 glycoprotein, a protein expressed on the surface of plasma cells. It antagonizes the function of CD38 via complement dependent cytotoxicity (CDC), antibody dependent cell mediated cytotoxicity (ADCC), and through apoptosis of CD38-expressing cells via cross-linking (de Weers, Journal of Immunology, 2011).
- b. **SAFETY:** Based on clinical trial data collected from patients with relapsed refractory multiple myeloma, the most common adverse events reported were infusion related, predominantly during the first infusion and up to 24 hours thereafter. Severe reactions, such as bronchospasm, dyspnea, hypoxia, and hypotension were rare (<2% each). Less serious and more common reactions (≥5%) included nasal congestion, cough, chills, rhinitis allergic, throat irritation, dyspnea and nausea. The incidence of any grade infusion reaction was 46% with the first infusion of daratumumab, 5% with the second infusion, and 4% with subsequent infusions. Of note, there were no grade 3 or higher reactions upon subsequent infusions. The median time to a reaction was approximately 1.5 hours while the incidence of infusion interruption due to an adverse event was 37%. Reactions could occur up to 48 hours following completion of the infusion. Common adverse events (≥10%) included, but not limited to: fatigue, cough, back pain, arthralgias, nausea and diarrhea. Serious adverse events were reported in up to 33% of patients and these included pneumonia (6%), general physical health deterioration (3%) and fever (3%). No grade 4 events were reported.

As of 11/15/18, daratumumab has been administered to approximately 4,407 patients in the setting of clinical trials, with an estimated world-wide post-marketing exposure of 34,316 person-years. HBV reaction, including fatal cases, has been observed in association with daratumumab. The overall frequency of HBV reactivation in daratumumab clinical trials, including serious and non-serious reports is 0.2%.

c. **PHARMACOLOGY**

Formulation: Daratumumab is administered intravenously.

Administration:

Infusion rates for daratumumab administration:

	Dilution volume	Initial rate (1 st hour)	Rate increment ^a	Maximum rate
First infusion	1000 mL	50 mL/hour	50 mL/hour every hour	200 mL/hour
Second infusion ^b	500 mL	50 mL/hour	50 mL/hour every hour	200 mL/hour
Subsequent infusion ^c	500 mL	100 mL/hour	50 mL/hour every hour	200 mL/hour

^a Consider incremental escalation of the infusion rate only in the absence of infusion reactions.

^b Use a dilution volume of 500 mL only if there were no Grade 1 (mild) or greater infusion reactions during the first 3 hours of the first infusion. Otherwise, continue to use a dilution volume of 1000 mL and instructions for the first infusion.

^c Use a modified initial rate for subsequent infusions (i.e. third infusion onwards) only if there were no Grade 1 (mild) or greater infusion reactions during a final infusion rate of ≥ 100 mL/hr in the first two infusions. Otherwise, continue to use instructions for the second infusion.

Daratumumab will be administered at the FDA-approved dose of 16mg/kg as an intravenous infusion. Weight from screening visit will be used for initial dosing and throughout treatment period but will be recalculated for weight change $\geq 10\%$. It will be administered weekly from weeks 1 to 8, followed by every 2 weeks from weeks 9 to 24, and then every 4 weeks thereafter until progression or unacceptable toxicities, for up to 24 months of total study therapy.

The first infusion of daratumumab (in 1000 mL) will be administered at an initial rate of 50 mL/hour to be escalated hourly by 50 mL/hour to a maximum rate of 200 mL/hour.

The second infusion of daratumumab will be administered in 500 mL if no grade 1 or greater reactions have occurred throughout the first 3 hours of the first infusion. The second infusion will be administered at an initial rate of 50 mL/hour to be escalated hourly by 50 mL/hour to a maximum rate of 200 mL/hour

The third and subsequent doses will be administered in 500 mL at a starting rate of 100 mL/hour to be escalated hourly by 50 mL/hour to a maximum rate of 200 mL/hour as long as no \geq Grade 1 infusion reactions occur during a final infusion rate of ≥ 100 mL/hr in the first two infusions.

Infusion reactions of any grade will lead to the temporary interruption or slowing of the infusion, as well as management of symptoms. Depending on the grade/severity of the reaction, this may require the permanent discontinuation of the drug.

Refer to section 8 for management of infusion reactions.

Supplier: Janssen Scientific Affairs, LLC

4.0 STAGING CRITERIA

Staging defined by NT-proBNP and troponin T cut-offs of < 332 pg/mL and < 0.035 ng/mL, respectively, as thresholds: Stage I, both under threshold; and Stage II, either troponin or NT-proBNP (but not both) over threshold and stage III, both elevated. If troponin T is not available, troponin I may be used, but threshold is < 0.1 ng/mL.

Stage IIIb cardiac disease is defined as NT-proBNP of > 8500 pg/mL (see exclusion criteria, section 5.2)

5.0 RECRUITMENT AND CONSENTING

The investigators will recruit participants from within their own practice. It is standard of care that patients scheduled for visits within the hematology/oncology clinics are "pre-screened" to determine if they may be "potentially eligible" for any available clinical trials. This is not specific for this study.

A screening consent is not obtained, as the pre-screening review is conducted prior to their appointment.

No data will be collected. The medical records are reviewed and a screening note is placed in the medical record to indicate that the patient may or may not be "potentially eligible" for a clinical trial. If the patient is potentially eligible, the physician will discuss the study at the visit. No procedures are performed for screening until after consent is obtained.

No data will be retained prior to obtaining consent. No data is collected during the "pre-screening". During the pre-screen, if a patient is determined to be not potentially eligible for any available clinical trials, the patient would not be considered as a "screen fail" as they have not undergone a full screening.

If potentially eligible, the investigator will inform the potential participant within his/her practice that he/she may be eligible for the research study. If the patient agrees to discuss and receive information about the study, an IRB-approved Informed Consent Form will be presented to the patient by a member of the research staff who will verbally outline the details of the procedures, risks, benefits, alternatives, costs, etc. The patient will be given the opportunity to bring the consent home and discuss with family members and/or other physicians and to ask any and all questions of the investigator and/or research staff. Once the patient is satisfied that all questions have been answered, if he/she wishes to participate, the consent form will be signed and dated by the patient and the person obtaining consent. Copies of the signed Informed Consent Form will be given to the patient and placed in the appropriate medical record. The original copy will be placed in the research chart.

For participants that live out of state, after the initial consent discussion in clinic, further discussions may take place via telephone with the research nurse and/or investigator to be sure all questions are answered to the patient's satisfaction. If the patient agrees to participate, (s)he may sign, print and date the consent document and fax it to the research office. The investigator will sign the consent on the day (s)he receives it, as confirmation that the consenting process has taken place. A copy of the document with both signatures will be given to the patient and placed in the appropriate medical record. The participant will be instructed to bring the document with their original signature to the next visit. In addition, when the patient returns to begin screening and/or treatment, a clean copy of the current consent is again presented to the patient for signature. The treating investigator will sign and a copy will be given to the patient. This signed consent as well as the original wet-ink signature pages (participant and investigator) will be kept in the research chart.

Potential participants who are non-English speaking will be consented using the Short Form (if IRB approved). A hospital translator or a translator on the phone line will be used throughout the consent process and throughout their participation in the study.

The consent process that has taken place will be documented in the medical record.

6.0 ELIGIBILITY CRITERIA

6.1 Eligibility Criteria

- Histological diagnosis of primary systemic (AL) amyloidosis:
 - a. At least one tissue demonstrating positive Congo Red staining with characteristic apple green birefringence AND/OR characteristic appearance of fibrils on electron microscopy **AND**
 - b. Evidence of a clonal plasma cell dyscrasia:
 - i. Monoclonal protein in the serum and/or urine by immunofixation electrophoresis **AND/OR**
 - ii. Abnormal serum free light chain assay **AND/OR**
 - iii. Clonal plasma cell population in the bone marrow demonstrated by immunohistochemistry, flow cytometry or in situ hybridization **AND**
 - c. Evidence of organ involvement other than carpal tunnel syndrome. Confirmation of tissue diagnosis at all sites of organ dysfunction is encouraged, but not required.
- Must have received at least one prior treatment regimen of proven efficacy in the treatment of AL amyloidosis. If prior treatment included ASCT, at least 6 months must have elapsed between ASCT and study drug.
- Must be ≥ 18 years of age.
- Must have a performance status of 0-2 by ECOG criteria (see Section 10.4)
- Must have adequate hepatic function as evidenced by serum bilirubin values < 2.0 mg/dL; ALT and/or AST $< 3 \times \text{ULN}$ (bilirubin < 3 mg/dL allowed if related to Gilbert's syndrome).
- Must have an absolute neutrophil count $\geq 1000/\text{mm}^3$, hemoglobin ≥ 7.5 g/dL, and platelet count $\geq 50 \times 10^9/\text{L}$

6.2 Exclusion Criteria:

- Renal Insufficiency (CrCL $< 20 \text{ mL/min}$), calculated by Cockcroft-Gault Equation
$$\text{CreatClear} = \text{Sex} * ((140 - \text{Age}) / (\text{SerumCreat})) * (\text{Weight} / 72)$$

*Equation parameters such as **Sex** have two or more discrete values that may be used in the calculation. The numbers in the parentheses, e.g. (1), represent the values that will be used.*

The default unit of measure for weight is kilograms. Please verify that the correct unit of measure has been selected.

<http://reference.medscape.com/calculator/creatinine-clearance-cockcroft-gault>
- Mayo clinic cardiac biomarker stage IIIb (see appendix 14.3)
- Evidence of significant cardiovascular conditions as specified below:
 - NT-ProBNP > 8500 ng/L (Mayo Stage IIIb patients are excluded)

- New York Heart Association (NYHA) classification IIIB or IV heart failure (see Section 10.5)
- Unstable Angina, Severe uncontrolled Arrhythmia refractory to medical management, prolonged QTc interval > 500 msec, symptomatic orthostatic hypotension refractory to medical management, or supine systolic blood pressure < 90 mm Hg.
- LVEF <30% by Echocardiogram
- Overt multiple myeloma (>30% bone marrow plasmacytosis, extensive (>2) lytic lesions, or hypercalcemia).
- Eligible for autologous stem cell transplant procedure (unless patient refuses)
- Any form of secondary or familial (ATTR) amyloidosis
- Active infection
- Prior treatment with daratumumab
- The presence or history of another malignancy is not allowed except for the following:
 - adequately treated basal cell or squamous cell skin cancer,
 - in situ cervical cancer,
 - adequately treated Stage I or II cancer from which the patient is currently in complete remission, any other cancer from which the patient has been disease-free for 5 years.
- Seropositive for human immunodeficiency virus (HIV)
- Seropositive for hepatitis B (defined by a positive test for hepatitis B surface antigen [HBsAg]). Subjects with resolved infection (ie, subjects who are HBsAg negative but positive for antibodies to hepatitis B core antigen [anti-HBc] and/or antibodies to hepatitis B surface antigen [anti-HBs]) must be screened using real-time polymerase chain reaction (PCR) measurement of hepatitis B virus (HBV) DNA levels. Those who are PCR positive will be excluded. EXCEPTION: Subjects with serologic findings suggestive of HBV vaccination (anti-HBs positivity as the only serologic marker) AND a known history of prior HBV vaccination, do not need to be tested for HBV DNA by PCR.
- Seropositive for hepatitis C (except in the setting of a sustained virologic response [SVR], defined as aviremia at least 12 weeks after completion of antiviral therapy)
- Pregnant or nursing women. Women and men of reproductive potential may not participate unless they have agreed to use an effective contraceptive method.
- Chronic smokers or those with known COPD with a FEV1 <50% of predicted normal. Note that FEV1 testing is required for chronic smokers or patients suspected of having COPD.
- Known moderate or severe persistent asthma within the past 2 years or currently has uncontrolled asthma of any classification

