No dosage adjustments are required for patients with pre-existing renal dysfunction. According to prior pharmacokinetic studies, no dosage adjustments are required for mild hepatic dysfunction (Total Bili 1.0-1.5x ULN or AST > ULN). Daratumumab has not been studied in patients with moderate or severe hepatic dysfunction (Total Bili > 1.5 x ULN). These patients will be excluded from the study (see exclusion criteria section 5.2).

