9.0 STUDY CALENDAR

	Screening	Prior to each dose	Monthly (CxD1)	Every 3 Month beginning C4,D1	End of Study Treatment Visit ⁵
PHYSICAL⁹					
History & Physical Exam, including liver assessment	X		X ⁷	X	X
Height	X				
ECOG Performance Status (see 10.4)	X	X		X	X
Vital Signs & Weight		X		X	
Adverse Event Monitoring		X		X	X
SF-36 (QOL)	X			X	
LABORATORY-Serum					
Complete Blood Count with Differential	X	X		X	X
Beta-HCG ¹	X				
Chemistry including: BUN, creatinine, glucose, sodium, potassium, chloride, bicarb, cholesterol, CK, calcium, total protein, LDH, magnesium, phosphorous, triglycerides, uric acid, TSH, amylase	X	X		X	X
BUN / Serum Creatinine	X	X		X	X
Creatinine Clearance ³	X				
Hepatic Function Testing: ALT/AST, Bilirubin, Albumin, Alkaline Phosphatase	X	X		X	X
β-2 Microglobulin / C-reactive protein	X			X	X
Cardiac enzymes: BNP/ Troponin I/NT ProBNP	X	X		X	X
Serum free light chain assay	X	X ⁸		X	X
SPEP, SIFE, Immunoglobulins	X			X	X
Coombs test; IAT (anti globulin test)	X				
Coagulation profile: PTT, INR, D-dimer, Factor X	X			X	X
HBV serology testing ¹⁰	X				
HBV DNA testing ¹¹	X				X
Type And Screen and blood bank phenotype ⁶	X				
Daratumumab-specific Immunofixation (patients with Kappa disease only)	X			X	X
LABORATORY-Urine					
Urinalysis	X			X	X
24 hour urine: total protein, creatinine, kappa, and lambda	X			X	X
UPEP / UIFE / TV	X			X	X
PATHOLOGY					
BM biopsy	X ²				
Fat aspirate (if not previously done)	X				
X-RAYS AND SCANS					
ECG / CXR	X				
Echocardiogram	X			Every 6 months	
PFTs (required for chronic smokers or known COPD)	X				

1 For women of childbearing potential only.

2 Bone marrow biopsy and aspiration must have been repeated following any previous therapy > 1 cycle.

3 CreatClear = Sex * ((140 - Age) / (SerumCreat)) * (Weight / 72); Equation parameters such as Sex have two or more discrete values that may be used in the calculation. The numbers in the parentheses, e.g. (1), represent the values that will be used. The default unit of measure for weight is kilograms. Please verify that the correct unit of measure has been selected. <http://reference.medscape.com/calculator/creatinine-clearance-cockcroft-gault>

4 While on study drug or until disease progression or start of another therapy.

5 30 days following last dose (+/-) 7 days.

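### As worded, the Section 6.1 hepatic criterion is met when only one of ALT and AST is below 3 x ULN, and no other item limits the second enzyme

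*Combined protocol and SAP*

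**What the plan says.** The hepatic entry criterion in Section 6.1 has two limbs: "Must have adequate hepatic function as evidenced by serum bilirubin values < 2.0 mg/dL; ALT and/or AST", the latter below 3 x ULN. Its only exception concerns bilirubin: "bilirubin < 3 mg/dL allowed if related to Gilbert's syndrome".

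Section 6.2 lists the exclusions. It covers hepatitis B, hepatitis C and active infection, but sets no limit on ALT or AST.

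Section 8.0 returns to liver function at its end. On dosing it says "no dosage adjustments are required for mild hepatic dysfunction (Total Bili 1.0-1.5x ULN or AST > ULN", with no upper bound on AST. It then says "Daratumumab has not been studied in patients with moderate or severe hepatic dysfunction (Total Bili > 1.5 x ULN", and that these patients are excluded, referring to exclusion criteria in Section 5.2.

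The Section 9.0 calendar has the line "Hepatic Function Testing: ALT/AST, Bilirubin, Albumin, Alkaline Phosphatase", marked at Screening, before each dose, every three months and at the end-of-treatment visit.

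**The concern.** This is an operative entry rule, and the choice of conjunction decides who passes it. If one enzyme is enough, the other has no limit at entry.

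Two things are at stake. The first is eligibility: two investigators could read the line differently and reach different decisions on the same patient. The second is attribution. Liver tests are read before every dose, and Section 8.0 delays dosing for most non-hematologic toxicity of Grade 3 or higher. Its listed exceptions refer to a condition present at baseline only for fatigue and asthenia, not for liver enzymes. A patient who enters with one clearly raised enzyme would need case-by-case judgement on whether a later value reflects the drug. Section 10.0 provides for assessing patients with hepatic involvement, so abnormal liver tests at entry are plausible.

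**Working it through.** The plan gives no figure to reproduce here. The check is a reading of the rule as a logical condition, followed by a search for any other limit.

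**1. The transaminase limb.** Assume the bilirubin limb is met. *Below* means below 3 x ULN.

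| ALT | AST | One enzyme suffices (*and/or* as written) | Both must qualify |
|---|---|---|---|
| below | below | meets | meets |
| below | at or above | meets | fails |
| at or above | below | meets | fails |
| at or above | at or above | fails | fails |

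The readings differ for every patient with exactly one enzyme at or above the limit.

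**2. How the protocol uses the conjunction.** Section 6.1 also has "Congo Red staining with characteristic apple green birefringence AND/OR characteristic appearance of fibrils on electron microscopy", where either finding alone is enough. The three proofs of clonality in the same list are joined in the same way. Where all parts are required (tissue, clonality, organ involvement), the section uses a plain AND. In Section 6.2, either hepatitis B antibody is enough to call for PCR testing, again under *and/or*. The protocol's own usage thus supports the reading in which one enzyme suffices.

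**3. Is only one enzyme measured?** No. The calendar puts ALT and AST on one line at Screening. It uses the slash elsewhere to list several tests, so availability does not explain the wording.

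**4. Is there another limit?**
- Section 6.2: no ALT or AST item.
- Section 8.0, mild dysfunction: AST above ULN, unbounded, and about dose adjustment rather than entry.
- Section 8.0, moderate or severe dysfunction: total bilirubin only.
- The cross-reference: Section 5.0 covers recruitment and consent and has no 5.2. Section 4.0 uses the same number for a cardiac exclusion that stands in 6.2, so 6.2 is probably meant. But 6.2 has no liver-function item.

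**5. The two bilirubin rules.** Section 6.1 uses 2.0 mg/dL (3 mg/dL with Gilbert's syndrome), and Section 8.0 uses 1.5 x ULN. The cut-offs coincide only if ULN is 2.0 / 1.5 = 1.33 mg/dL, or 3 / 1.5 = 2.0 mg/dL under the exception. The documents give no ULN. The two sections therefore need reconciling on bilirubin too.

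**6. Scale.** No rate of discordant enzymes is given. For scale only, one patient is 1/25 = 4% of planned enrolment, 1/20 = 5% of the evaluable target, or 1/5 = 20% of the interim cohort. These are shares of one patient, not estimates of how many are affected.

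**The case against.** The strongest reply is that this is loose drafting with little consequence. The criterion requires adequate hepatic function, with laboratory values as evidence, so an investigator could refuse a patient with a very high enzyme on that ground. The bilirubin limb, the hepatitis items and the active-infection item narrow the group further. All of that is fair, but none of it sets a transaminase limit.

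A reader might infer that a high entry value would corrupt the safety results. The documents do not support that:
- The primary objective (Sections 1.0 and 11.3) is safety and tolerability specifically with respect to infusion reactions.
- The interim triggers in Section 11.2 count drug-related Grade 4 or 5 events and Grade 3 infusion reactions. A pre-existing raised enzyme enters neither directly.
- Section 12.1.3 counts occurrences that are new or worse than baseline, so a stable raised enzyme does not fit.
- Section 8.0 asks that drug toxicity be distinguished from other illness and amyloid symptoms, places the delay criteria under drug-related toxicity, and allows restart on recovery to Grade 2 or baseline.

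The analysis sets are barely touched. Section 11.3 mentions all eligible subjects, but defines the safety population by receipt of at least one dose and uses it for safety and efficacy alike.

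What remains is an unclear entry rule with no backstop, and some difficulty of attribution in any patient it admits.

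**Conclusion.** The point holds as a defect in an entry criterion. As worded, one transaminase below 3 x ULN is enough, and neither Section 6.2 nor Section 8.0 limits the other. This rests on reading *and/or* as Section 6.1 uses it elsewhere, and on the bilirubin limb being met.

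A reader might also infer that the sponsor-investigator intended both enzymes to be below the limit, so that the text is a proven error. No section states that intent, so it should be put as a question. Nor do the documents give grade thresholds for transaminases, so calling a particular entry value severe would be an assumption.

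The size is modest. The number of patients affected cannot be derived, no stated figure changes, and the infusion-reaction endpoint is unaffected. It still merits correction because it governs who is exposed to the drug and can be settled with tests already scheduled.

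**What to change.** The sponsor-investigator should replace *and/or* in Section 6.1 with wording that says whether one or both enzymes must meet the protocol's existing limit. If both must, *ALT and AST each < 3 x ULN* keeps the protocol's own number.

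At the same time, reconcile Section 6.1 with the hepatic exclusion in Section 8.0: correct the reference to Section 5.2, decide whether the exclusion belongs in the Section 6.2 list, and align the two bilirubin rules.

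If accrual is complete, record which reading was applied and check enrolled patients' Screening ALT and AST against it.

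The cost is a short wording amendment and no new test. If both enzymes must qualify, a rare patient with one raised enzyme may not be enrolled.
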